### **6.8.2.6 I-NRS at Day 85**

The change from Baseline to Day 85 in the I-NRS score will be summarized with descriptive statistics.

Summary statistics will also be presented for the change from Baseline in I-NRS at each timepoint (Day 15, Day 29, Day 57 and Day 85). Additionally, summary statistics for I-NRS will be presented at each timepoint (Baseline, Day 15, Day 29, Day 57 and Day 85).

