6.3.2. Baseline Visit

If the subject is deemed eligible and proceeds to enrollment on the same day, in addition to the screening assessments the following will be conducted:

- Collect blood sample for CBC and chemistry
- Collect urine sample for urinalysis
- Assess Signs of AD prior to application of study drug
- Collect EASI score prior to application of study drug
- Collect I-NRS prior to application of study drug
- Randomize subject to study drug treatment
- Apply study drug on subject's AD lesions (see Section 5.1.5)
- Monitor subject for AEs 15 minutes after application of study drug
- Photographs and Signs of AD scoring of target lesion (selected sites only)
- Train subject in proper application of study drug
- Weigh and dispense study drug
- Dispense study diary (Day 1 through Day 28) and train the subject in entering administration times and daily pruritus score.

If the subject is not enrolled on the same day as the Screening Visit, the following will be conducted at the Baseline Visit:

- Review eligibility criteria
- Review medical history and review of systems
- Query subject for adverse events since the signing of the informed consent/assent and changes in concomitant medications
- Collect blood sample for CBC and chemistry
- Collect urine sample for urinalysis
- Conduct UPT (WOCBP only)
- Collect urine sample for UDS
- Perform IGA prior to application of study drug
- Calculate BSA of total AD involvement
- Assess Signs of AD score prior to application of study drug
- Collect EASI score prior to application of study drug
- Collect I-NRS prior to application of study drug
- Photographs and Signs of AD scoring of target lesion (selected sites only)
- Randomize subject to study drug treatment
- Apply study drug on subject's AD lesions (see Section 5.1.5)
- Monitor subject for AEs 15 minutes after application of study drug
- Train subject in proper application of study drug
- Weigh and dispense study drug

- Dispense study diary (Day 1 through Day 28) and train the subject in entering administration times and daily pruritus score.

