9.3. Description of Statistical Methods

9.3.1. General Approach

This study will be evaluated using 3 analysis sets: intent-to-treat (ITT), per protocol (PP), and safety. Efficacy conclusions will be drawn from the ITT analysis set. The ITT analysis set will consist of all randomized subjects with at least one post-baseline efficacy assessment and will be based on randomized study group, regardless of study drug received. The PP analysis set will be used to support the efficacy findings in the ITT analyses and will include subjects with no major protocol deviations. Safety conclusions will be drawn from the safety analysis set. The safety analysis set will include all subjects that received at least one application of study drug and had at least one post-baseline safety assessment with treatment based on study drug received regardless of randomization group.

Demographics will be summarized using the safety analysis set by baseline age, gender, race, ethnicity, height, and weight. The primary efficacy analysis will be conducted on the ITT population. For continuous variables, the mean, standard deviation (SD), median, and range will be presented along with the 95% confidence interval (CI). Categorical variables will be summarized by proportions along with the 95% CI.

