9.3.3. Efficacy Analyses

The efficacy variables include the IGA, BSA of AD, Signs of AD score, EASI score, and pruritus scores (I-NRS) collected at Screening/Baseline and all subsequent study visits and the WI-NRS recorded daily by subjects.

The primary efficacy endpoint for the study is the proportion of subjects with IGA success defined as an IGA score of Clear (0) or Almost Clear (1) with at least a 2-grade improvement from Baseline at Day 85. The IGA will be dichotomized into “success” and “failure” at study Day 15, Day 29, Day 57, and Day 85. Success on IGA defined as a score of Clear (0) or Almost Clear (1) and at least a 2-grade improvement from Baseline at Day 15, Day 29, Day 57, and Day 85 will be analyzed using logistic regression, adjusting for Baseline IGA.

Summary statistics will be prepared for the change from Baseline in the percent of BSA affected by AD at Days 15, 29, 57, and 85. The change from Baseline in BSA of AD will be analyzed using ANCOVA with Baseline BSA of AD and treatment as covariates.

Summary statistics will be presented for the change from baseline in each of the Signs of AD scores (erythema, exudation, excoriation, induration/papulation, and lichenification) at each timepoint (Day 15, Day 29, Day 57 and Day 85). A total score will be calculated based on the sum of each of the Signs of AD (0, 1, 2, or 3; max score of 15) and the change from baseline will be summarized for each timepoint. The change from baseline in Signs of AD score at Day 15, Day 29, Day 57, and Day 85 will be analyzed using ANCOVA with Baseline Signs of AD score and treatment as covariates.

The proportion of subjects with an EASI 50 and EASI 75 score will be summarized at Day 15, Day 29, Day 57, and Day 85 and compared using logistic regression, adjusting for Baseline EASI score. Summary statistics will be prepared for the change from Baseline in the EASI score and I-NRS at each timepoint (Day 15, Day 29, Day 57 and Day 85).

Summary statistics will be prepared for the change from Baseline in the Signs of AD score for the target lesion (selected sites) at each timepoint (Day 15, Day 29, Day 57 and Day 85).

Summaries of the pruritus scores (WI-NRS) reported by the subjects in the daily Patient Diary will be presented using daily means by treatment and with graphic presentations.

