### **5.1.2 Secondary Efficacy Endpoints**

The secondary efficacy endpoints for the study are:

- The change from Baseline in the total Signs of AD score at Day 85,
- The proportion of subjects with an IGA of Clear or Almost Clear at Day 85,
- The proportion of subjects with at least a 2-grade improvement in IGA from Baseline at Day 85,
- The change from Baseline in the percent of total body surface area (BSA) affected by AD at Day 85,
- The time to achieve IGA success, and
- The change from Baseline to Day 85 in the Itch-Numerical Rating Scale (I-NRS).

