## **6. STATISTICAL AND ANALYTICAL PLANS**

### **6.1 General Methodology**

All statistical processing will be performed using SAS® 9.4 or higher. No interim analyses are planned. This Phase 2 study is designed to identify the response of BTX 1204 4.0% BID compared to Vehicle BID. Statistical tests will be exploratory. No adjustments for Type I error will occur.

Descriptive statistics will be used to provide an overview of the efficacy and safety results. For categorical parameters, the number and percentage of subjects in each category will be presented. For continuous parameters, descriptive statistics will include n (number of subjects), mean, standard deviation (SD), median, minimum and maximum.

The primary method of handling missing efficacy data in the Intent-to-Treat (ITT) and modified Intent-to-Treat (mITT) analysis sets will be based on last observation carried forward (LOCF). Repeated measures analyses will be used on the observed data as a sensitivity analysis on the primary endpoint.

The efficacy analysis performed on the ITT population is considered the primary analysis. The efficacy analyses performed on the mITT and per-protocol (PP) populations are considered supportive analyses.

The number of subjects in each analysis set will be summarized. Reasons for study withdrawal during the study will be summarized using frequencies and percentages by treatment group.

Reported AEs, medical history terms and prior and concomitant procedures and therapies will be classified on the basis of Medical Dictionary for Regulatory Activities (MedDRA) terminology. Prior and concomitant medications will be classified on the basis of World Health Organization Drug Dictionary (WHO-DDE) terminology.

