#### **6.1.4 Adjustments for Covariates**

Baseline total BSA affected by AD will be a covariate for the secondary efficacy endpoint, change from Baseline in total BSA affected by AD. Baseline Signs of AD total score will be a covariate for the secondary and exploratory efficacy endpoints change from Baseline in total Signs of AD. No other covariates are planned to be used in the analyses for this study.

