Table 14.2.2.4.2: Secondary Endpoint: Time to IGA Success (mITT Population)

Table 14.2.2.4.3: Secondary Endpoint: Time to IGA Success (PP Population)

Table 14.2.2.5.1: Secondary Endpoint: Summary of Itching-Numerical Rating Score by Visit  
(ITT Population)  
(Page 1 of 3)

	BTX 1204 4% BID (N=xxx)	Vehicle BID (N=xxx)
How would you rate your average itch in the past 24 hours?		
Baseline		
n	xx	xx
Mean	xx.x	xx.x
SD	xx.xx	xx.xx
Median	xx.x	xx.x
Min., Max.	xx, xx	xx, xx
Day 15		
n	xx	xx
Mean	xx.x	xx.x
SD	xx.xx	xx.xx
Median	xx.x	xx.x
Min., Max.	xx, xx	xx, xx
Change from Baseline		
n	xx	xx
Mean	xx.x	xx.x
SD	xx.xx	xx.xx
Median	xx.x	xx.x
Min., Max.	xx, xx	xx, xx

Note: Missing values are imputed using LOCF.

SOURCE: USERNAME/SPONSOR/PROJECT/JOBNAME (DATE,TIME)

Table 14.2.2.5.1: Secondary Endpoint: Summary of Itching-Numerical Rating Score by Visit  
(ITT Population)  
(Page 2 of 3)

	BTX 1204 4% BID (N=xxx)	Vehicle BID (N=xxx)
How would you rate your average itch in the past 24 hours?		
Day 29		
n	xx	xx
Mean	xx.x	xx.x
SD	xx.xx	xx.xx
Median	xx.x	xx.x
Min., Max.	xx, xx	xx, xx
Change from Baseline		
n	xx	xx
Mean	xx.x	xx.x
SD	xx.xx	xx.xx
Median	xx.x	xx.x
Min., Max.	xx, xx	xx, xx
Day 57		
n	xx	xx
Mean	xx.x	xx.x
SD	xx.xx	xx.xx
Median	xx.x	xx.x
Min., Max.	xx, xx	xx, xx
Change from Baseline		
n	xx	xx
Mean	xx.x	xx.x
SD	xx.xx	xx.xx
Median	xx.x	xx.x
Min., Max.	xx, xx	xx, xx

Note: Missing values are imputed using LOCF.  
SOURCE: USERNAME\SPONSOR\PROJECT\JOBNAME (DATE,TIME)

Table 14.2.2.5.1: Secondary Endpoint: Summary of Itching-Numerical Rating Score by Visit  
 (ITT Population)  
 (Page 3 of 3)

	BTX 1204 4% BID (N=xxx)	Vehicle BID (N=xxx)
How would you rate your average itch in the past 24 hours?		
Day 85		
n	xx	xx
Mean	xx.x	xx.x
SD	xx.xx	xx.xx
Median	xx.x	xx.x
Min., Max.	xx, xx	xx, xx
Change from Baseline		
n	xx	xx
Mean	xx.x	xx.x
SD	xx.xx	xx.xx
Median	xx.x	xx.x
Min., Max.	xx, xx	xx, xx

Note: Missing values are imputed using LOCF.

SOURCE: USERNAME/SPONSOR/PROJECT/JOBNAME (DATE,TIME)

Repeat Table 14.2.2.5.1 for the following:

Table 14.2.2.5.2: Secondary Endpoint: Summary of Itching-Numerical Rating Score by Visit (mITT Population)

Table 14.2.2.5.2: Secondary Endpoint: Summary of Itching-Numerical Rating Score by Visit (PP Population)

**Programming note:** *Replace footnote with* - Note: No imputations were made for missing data.

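### The secondary itch endpoint (I-NRS change at Day 85) has no pre-specified between-arm estimate, interval or baseline adjustment, unlike the other two continuous secondary endpoints

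*SAP*

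**What the plan says.** Protocol 3.2 and SAP 5.1.2 both list I-NRS change from Baseline to Day 85 as a secondary endpoint. For its analysis, SAP 6.8.2.6 says: "The change from Baseline to Day 85 in the I-NRS score will be summarized with descriptive statistics". It adds by-visit summaries and nothing else. SAP 6.1 defines the content: "For continuous parameters, descriptive statistics will include n (number of subjects), mean, standard deviation (SD), median, minimum and maximum". The shell for Table 14.2.2.5.1 has one column per arm, with those statistics for each visit and for change from Baseline. It has no difference, LS mean, interval or p-value.

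SAP 6.1.4 names baseline BSA and baseline Signs of AD as covariates, then states: "No other covariates are planned to be used in the analyses for this study". SAP 6.8.2.1 (Signs of AD) and 6.8.2.4 (BSA) use those covariates in ANCOVA models with treatment as a factor.

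The protocol matches the SAP on itch. Section 9.3.3 says: "Summary statistics will be prepared for the change from Baseline in the EASI score and I-NRS at each timepoint". Baseline data will exist, because Protocol 6.3.2 instructs sites: "Collect I-NRS prior to application of study drug".

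**The concern.** I-NRS has the same structure as the two endpoints that are modelled: a score taken before first application and again at Days 15, 29, 57 and 85, analysed as change from Baseline. Neither document explains why it is treated differently. SAP 6.1.8 gives the trial's purpose as identifying the response relative to vehicle, and that calls for a contrast.

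I-NRS is the only patient-reported secondary endpoint, and the only patient-reported efficacy endpoint listed in SAP 5.1. With the table as planned, readers will subtract two raw mean changes. That difference comes without a stated interval and is exposed to chance imbalance in baseline itch. Anyone wanting an adjusted figure would have to choose the method after seeing the data.

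**Working it through.** **No plan figure to reproduce.** Protocol 9.4 and SAP 7 size the trial on clinical considerations. They give no SD, correlation, target difference or power for any endpoint. The only document input is 100 subjects per arm; the rest are assumptions.

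**Assumptions.** I-NRS SD of 2.5 at both Baseline and Day 85; baseline to Day 85 correlation ρ of 0.3, 0.5 or 0.7; no loss of subjects; normal 95% limits.

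**Formulas for the 95% CI half-width of the between-arm difference.**
- Raw change: 1.96 × SD × √(2(1−ρ)) × √(2/n)
- ANCOVA on baseline: 1.96 × SD × √(1−ρ²) × √(2/n)
- Variance ratio, ANCOVA to raw change: (1−ρ²) / (2(1−ρ)) = (1+ρ)/2

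With n = 100, the common factor is 1.96 × 2.5 × √0.02 = 0.693.

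| ρ | Raw change | ANCOVA | Variance ratio |
|---|---|---|---|
| 0.3 | 0.693 × √1.4 = 0.82 | 0.693 × √0.91 = 0.66 | 0.65 |
| 0.5 | 0.693 × √1.0 = 0.69 | 0.693 × √0.75 = 0.60 | 0.75 |
| 0.7 | 0.693 × √0.6 = 0.54 | 0.693 × √0.51 = 0.49 | 0.85 |

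**Sensitivity to the SD and to losses.** At SD 2.0 and ρ 0.6, the half-widths are 0.44 (ANCOVA) and 0.50 (raw change). At SD 3.0 and ρ 0.3, they are 0.79 and 0.98. With 85 per arm (an assumed 15% loss), SD 2.5 and ρ 0.5, they are 0.65 and 0.75.

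**Exposure to baseline imbalance.** With equal SDs, a chance baseline difference d shifts the raw-change comparison by (1−ρ) × d in size. The standard error of d is 2.5 × √0.02 = 0.35. A one-standard-error imbalance therefore moves the raw comparison by 0.7 × 0.35 = 0.25 points at ρ 0.3, 0.18 at ρ 0.5 and 0.11 at ρ 0.7. ANCOVA removes this shift.

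**What the planned table still allows.** It prints n, mean and SD of change for each arm, so the unadjusted difference has standard error √(SD₁²/n₁ + SD₂²/n₂) and an interval follows. If the same subjects contribute at both visits, the three printed SDs also give the within-arm covariance, (SD_base² + SD_Day85² − SD_change²)/2, and hence an approximate adjusted estimate. The shell prints means to one decimal, so a difference of two means can be off by up to 0.05 + 0.05 = 0.1 points. Either figure would be the reader's own reconstruction, not a planned result.

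**The case against.** The strongest reply is that this is a deliberate and consistent choice in an exploratory Phase 2a trial. The SAP follows the protocol. Protocol 9.2 says no assessment will use hypothesis testing and allows post-hoc analyses to be described in the study report. Entry criteria set no minimum itch score, which could be a reason to keep itch descriptive, though neither document says so.

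Part of this stands: there is no contradiction between the documents on the I-NRS analysis, and the choice does not touch the primary analysis. But an LS mean difference with a confidence interval is estimation, so Protocol 9.2 does not stand in its way. Both documents already plan models for other endpoints.

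Four stronger readings may tempt a reader, and the documents do not support them.
- That the trial allows no treatment comparison for itch. Arm-level n, mean and SD are tabulated, so an unadjusted difference and interval can be derived, and any baseline imbalance will be visible.
- That the SAP dropped a comparison the protocol promised. Protocol 9.3.3 plans summaries only. Protocol 9.3.1 does say: "For continuous variables, the mean, standard deviation (SD), median, and range will be presented along with the 95% confidence interval (CI". SAP 6.1 and the shell omit that interval, and SAP 8 does not list the omission, but the protocol does not say the interval is for the between-arm difference.
- That I-NRS alone among secondary endpoints lacks a comparison. Time to IGA success (SAP 6.8.2.5) gets Kaplan-Meier summaries with no test or hazard ratio. I-NRS is the only continuous one left unmodelled.
- That every visit should be modelled. I-NRS change at Days 15, 29 and 57 is in no endpoint list. Modelling four visits in three populations would mean 4 × 3 = 12 unadjusted comparisons.

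**Conclusion.** The point holds as a modest weakness in the choice of analysis, shared by both documents. A listed secondary endpoint has no pre-specified between-arm estimate, no interval and no baseline adjustment, while its two continuous companions have a baseline-adjusted model.

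The loss is pre-specification, protection against baseline imbalance, and some precision. Under SD 2.5 and 100 per arm, adjustment narrows the half-width by about 0.16 points at ρ 0.3 (0.82 to 0.66), 0.09 at ρ 0.5 (0.69 to 0.60) and 0.04 at ρ 0.7 (0.537 to 0.495), on a 0 to 10 scale. These sizes rest wholly on the assumed SD and correlation. That the comparison is missing rests on the text alone.

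**What to change.** Before unblinding:
- SAP 6.8.2.6: analyse I-NRS change from Baseline to Day 85 by ANCOVA, with baseline I-NRS as covariate and treatment as factor. Report the LS mean difference with 95% CI as an exploratory estimate.
- SAP 6.1.4: add baseline I-NRS to the covariates.
- Table 14.2.2.5.1 and its mITT and PP repeats: add rows for the Day 85 difference and its CI. Copying the Signs of AD or BSA shells is not enough, since they show an LS mean, a standard deviation and a p-value but no difference or interval.
- SAP 8: record the addition, since Protocol 9.3.3 plans summaries only.
- Leave Days 15, 29 and 57 descriptive.

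The model form is already specified for two other endpoints and no new data are needed. The small downside is one further unadjusted exploratory comparison in each of the ITT, mITT and PP populations. Giving the estimate and interval without a p-value keeps it to estimation.

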## **6.9 Exploratory Efficacy Analysis**

### **6.9.1.1 Signs of Atopic Dermatitis at Days 15, 29 and 57**

The change from Baseline in the Signs of AD total score for the target lesion at Day 15, Day 29, and Day 57 will be analyzed using ANCOVA with Baseline score as a covariate and treatment as a factor.

Summary statistics will also be presented for the change from Baseline in each of the Signs of AD scores (erythema, exudation, excoriation, induration/papulation, and lichenification) and total score at each timepoint (Day 15, Day 29, Day 57 and Day 85).

Summary statistics for each of the Signs of AD scores (erythema, exudation, excoriation, induration/papulation, and lichenification) and total score at each timepoint will be presented (Baseline, Day 15, Day 29, Day 57 and Day 85).

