3.2. Study Endpoints

The primary endpoint for the study is the proportion of subjects with an Investigator's Global Assessment (IGA) success defined as an IGA score of "Clear" (0) or "Almost Clear" (1) with at least a 2-grade improvement from Baseline at Day 85.

The secondary endpoints for the study are:

- The proportion of subjects with an EASI 75 score at Day 85,
- The proportion of subjects with an EASI 50 score at Day 85,
- The change from Baseline in the Signs of AD score at Day 85,
- The proportion of subjects with an IGA of Clear or Almost Clear at Day 85,
- The proportion of subjects with at least a 2-grade improvement in ISGA from Baseline at Day 85,
- The change from Baseline in the percent of body surface area (BSA) affected by AD at Day 85,
- The time to achieve IGA success, and
- The change from Baseline to Day 85 in the Itch-Numerical Rating Scale (I-NRS)

Exploratory analyses will be conducted for:

- The change from Baseline in the Signs of Atopic Dermatitis score at Day 15, Day 29, and Day 57,
- The change from Baseline in the percent of body surface area (BSA) affected by AD at Day 15, Day 29, and Day 57,
- The proportion of subjects with IGA success defined as an IGA score of "Clear" (0) or "Almost Clear" (1) with at least a 2-grade improvement from Baseline at Day 15, Day 29, and Day 57,
- The absolute and percent change from Baseline in the Eczema Area Severity Index (EASI) score at Day 15, Day 29, Day 57, and Day 85,

- Change from Baseline in the subject's reports of pruritus obtained daily on a Patient Diary,
- Time to improvement of pruritus (change of ≥ 4 in the Worst Itch Numerical Rating Score [WI-NRS, 0 – 10 score]),
- Subject's assessment of the change in their AD from Baseline to Day 85 (Patient Reported Outcome [PRO]), and
- The change from Baseline to Day 29, and Day 57, and Day 85 in the Signs of AD score for the target lesion (selected sites).

Safety outcome measures to be assessed are:

- Reported adverse events (AEs) including treatment-emergent (TEAE) monitored from time of consent through the end of study,
- Changes in clinical labs including complete blood count (CBC), chemistry, and urinalysis between Baseline and Day 85, and
- Subject's reports of burning/stinging obtained during visits on Day 1, Day 15, Day 29, Day 57, and Day 85.

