The Signs of AD score will be an examination of all lesions on the subject for the presence of erythema, exudation, excoriation, induration/papulation, and lichenification. Each sign will be graded according to the grade and definitions provided in Table 3.

Table 3 Signs of Atopic Dermatitis (Paller)

Score	Grade	Definition
Erythema (redness)		
0	None	No redness
1	Mild	Mildly detectable erythema; pink
2	Moderate	Dull red; clearly distinguishable
3	Severe	Deep, dark red; marked and extensive
Exudation (oozing and crusting)		
0	None	No oozing or crusting
1	Mild	Minor or faint signs of oozing
2	Moderate	Definite oozing or crusting
3	Severe	Marked and extensive oozing or crusting
Excoriation (evidence of scratching)		
0	None	No evidence of excoriation
1	Mild	Mild excoriation
2	Moderate	Definite excoriation
3	Severe	Marked, deep, or extensive excoriation
Induration/papulation		
0	None	None
1	Mild	Slightly perceptible elevation
2	Moderate	Clearly perceptible elevation but not extensive
3	Severe	Marked and extensive elevation
Lichenification (epidermal thickening)		
0	None	No epidermal thickening
1	Mild	Minor epidermal thickening
2	Moderate	Moderate epidermal thickening; accentuated skin lines
3	Severe	Severe epidermal thickening; deeply accentuated skin lines

The EASI score will be conducted by the principal investigator or an appropriately trained designee to obtain a score to measure the extent (area) and severity of AD. EASI will be scored using the area score for each of the four regions (head and neck, trunk, upper limbs, and lower limbs) of the body. The area score is the percentage of skin affected by atopic dermatitis (eczema) for each body region:

Area score: Percentage of skin affected by eczema in each region

0	No active eczema in this region
1	1–9%
2	10–29%
3	30–49%
4	50–69%
5	70–89%
6	90–100%: the entire region is affected by eczema

At each study visit, the subject will complete the Itch Numeric Rating Score (I-NRS).

I-NRS

The subject will be asked, “How would you rate your AVERAGE itch in the past 24 hours, on a scale from 0 to 10, where 0 is No itch and 10 is Worst itch imaginable?”

Prior to morning application of the study drug, the subject will record in their diary the Worst Itch Numeric Rating Score (WI-NRS).

Each day the subject will complete the Worst-Itch Numeric Rating Score (WI-NRS).

WI-NRS

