### **5.1.3 Exploratory Efficacy Endpoints**

The exploratory endpoints for the study are:

- The change from Baseline in the total Signs of AD score at Day 15, Day 29, and Day 57,
- The change from Baseline in the percent of total BSA affected by AD at Day 15, Day 29, and Day 57
- The proportion of subjects with IGA success defined as an IGA score of “Clear: (0) or “Almost Clear” (1) with at least a 2-grade improvement from Baseline at Day 15, Day 29, and Day 57,
- The change from Baseline to Day 29 and Day 57, and Day 85 in the Signs of AD score for the target lesion (at selected sites only).

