### **6.9.1.2 Percent of Total Body Surface Area Affected by Atopic Dermatitis at Days 15, 29 and 57**

Change from Baseline in the percent of total BSA affected by AD at Days 15, 29, and 57 will be analyzed using ANCOVA with Baseline percent of total BSA affected by AD as covariate and treatment as factor.

Summary statistics will be presented for the percent of total BSA affected by AD and change from Baseline at each timepoint (Day 15, Day 29, Day 57 and Day 85).

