 SOURCE: USERNAME/SPONSOR/PROJECT/JOBNAME (DATE,TIME)

Table 14.2.3.2.1: Exploratory Efficacy Endpoint: Summary of Signs of AD Score by Visit  
(ITT Population)  
(Page 2 of x)

	BTX 1204 4% BID (N=xxx)	Vehicle BID (N=xxx)
Erythema		
Day 29		
n	xx	xx
Mean	xx.x	xx.x
SD	xx.xx	xx.xx
Median	xx.x	xx.x
Min., Max.	xx, xx	xx, xx
Change from Baseline		
n	xx	xx
Mean	xx.x	xx.x
SD	xx.xx	xx.xx
Median	xx.x	xx.x
Min., Max.	xx, xx	xx, xx
Day 57		
n	xx	xx
Mean	xx.x	xx.x
SD	xx.xx	xx.xx
Median	xx.x	xx.x
Min., Max.	xx, xx	xx, xx
Change from Baseline		
n	xx	xx
Mean	xx.x	xx.x
SD	xx.xx	xx.xx
Median	xx.x	xx.x
Min., Max.	xx, xx	xx, xx

Note: Missing values are imputed using LOCF.

SOURCE: USERNAME\SPONSOR\PROJECT\JOBNAME (DATE,TIME)

**Programming note:** Continue for Exudation, Excoriation, Induration/Papulation, Lichenification, and Total Score

Repeat Table 14.2.3.2.1 for the following:

Table 14.2.3.2.2: Exploratory Efficacy Endpoint: Summary of Signs of AD Score by Visit (mITT Population)

Table 14.2.3.2.3: Exploratory Efficacy Endpoint: Summary of Signs of AD Score by Visit (PP Population)

**Programming note:** *Replace footnote with* - Note: No imputations were made for missing data.

Table 14.2.3.3.1: Exploratory Endpoint: Change from Baseline in Percent of Total BSA Affected by AD at Days 15, 29 and 85  
(ITT Population)  
(Page 1 of 2)

	BTX 1204 4% BID (N=xxx)	Vehicle BID (N=xxx)	Treatment P-Value
Change from Baseline in Total BSA affected by AD			
Day 29			
n	xx	xx	
Mean	xx.x	xx.x	
SD	xx.xx	xx.xx	
Median	xx.x	xx.x	
Min., Max.	xx, xx	xx, xx	
LSMean a	xx.x		x.xxx a
LSSD a	xx.xx		
Day 57			
n	xx	xx	
Mean	xx.x	xx.x	
SD	xx.xx	xx.xx	
Median	xx.x	xx.x	
Min., Max.	xx, xx	xx, xx	
LSMean a	xx.x		x.xxx a
LSSD a	xx.xx		

a Least squares mean, standard deviation, and p-value from an analysis of covariance with baseline Total Signs of AD and treatment as covariates.

Note: Missing values imputed using LOCF.

SOURCE: USERNAME/SPONSOR/PROJECT\JOBNAME (DATE, TIME)

Table 14.2.3.3.1: Exploratory Endpoint: Change from Baseline in Percent of Total BSA Affected by AD at Days 15, 29 and 85  
 (ITT Population)  
 (Page 2 of 2)

	BTX 1204 4% BID (N=xxx)	Vehicle BID (N=xxx)	Treatment P-Value
Change from Baseline in Total BSA affected by AD			
Day 57			
n	xx	xx	
Mean	xx.x	xx.x	
SD	xx.xx	xx.xx	
Median	xx.x	xx.x	
Min., Max.	xx, xx	xx, xx	
LSMean a	xx.x		x.xxx a

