Note: Missing values are imputed using LOCF.

SOURCE: USERNAME\SPONSOR\PROJECT\JOBNAME (DATE,TIME)

Repeat Table 14.2.3.6.1 for the following:

Table 14.2.3.6.2: Summary of Investigator Global Assessment by Visit (mITT Population)

Table 14.2.3.6.3: Summary of Investigator Global Assessment by Visit (PP Population)

**Programming note:** *Replace footnote with* - Note: No imputations were made for missing data.

Table 14.2.3.7.1: Exploratory Endpoint: Change from Baseline in Signs of AD Total Score at Target Lesions at Days 29, 57 and 85  
(ITT Population)  
(Page 1 of 2)

	BTX 1204 4% BID (N=xxx)	Vehicle BID (N=xxx)	Treatment P-Value
Change from Baseline in Total Signs of AD			
Day 29			
n	xx	xx	
Mean	xx.x	xx.x	
SD	xx.xx	xx.xx	
Median	xx.x	xx.x	
Min., Max.	xx, xx	xx, xx	
LSMean a	xx.x		x.xxx a
LSSD a	xx.xx		
Day 57			
n	xx	xx	
Mean	xx.x	xx.x	
SD	xx.xx	xx.xx	
Median	xx.x	xx.x	
Min., Max.	xx, xx	xx, xx	
LSMean a	xx.x		x.xxx a
LSSD a	xx.xx		

a Least squares mean, standard deviation, and p-value from an analysis of covariance with baseline Total Signs of AD and treatment as covariates.

Note: Missing values imputed using LOCF.

SOURCE: USERNAME\SPONSOR\PROJECT\JOBNAME (DATE, TIME)

Table 14.2.3.7.1: Exploratory Endpoint: Change from Baseline in Signs of AD Total Score at Target Lesions at Days 29, 57 and 85  
(ITT Population)  
(Page 2 of 2)

	BTX 1204 4% BID (N=xxx)	Vehicle BID (N=xxx)	Treatment P-Value
Change from Baseline in Total Signs of AD			
Day 29			
n	xx	xx	
Mean	xx.x	xx.x	
SD	xx.xx	xx.xx	
Median	xx.x	xx.x	
Min., Max.	xx, xx	xx, xx	
LSMean a	xx.x		x.xxx a
LSSD a	xx.xx		

a Least squares mean, standard deviation, and p-value from an analysis of covariance with baseline Total Signs of AD and treatment as covariates.

Note: Missing values imputed using LOCF.

SOURCE: USERNAME\SPONSOR\PROJECT\JOBNAME (DATE, TIME)

Repeat Table 14.2.3.7.1 for the following:

Table 14.2.3.7.2: Exploratory Endpoint: Change from Baseline in Signs of AD Total Score at Target Lesions at Days 29, 57 and 85 (mITT Population)

Table 14.2.3.7.3: Exploratory Endpoint: Change from Baseline in Signs of AD Total Score at Target Lesions at Days 29, 57 and 85 (PP Population)

**Programming note:** *Replace footnote with* - Note: No imputations were made for missing data.

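### SAP 6.9.1.1 puts the exploratory Signs ANCOVA on the target lesion, and two sets of exploratory shells carry wrong days or the wrong covariate, so text and shells conflict and could misdirect programming

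*SAP*

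**What the plan says.** **Signs of AD, Days 15, 29 and 57.** SAP 5.1.3 lists the exploratory endpoint as "The change from Baseline in the total Signs of AD score at Day 15, Day 29, and Day 57", and Protocol 3.2 as "The change from Baseline in the Signs of Atopic Dermatitis score at Day 15, Day 29, and Day 57". Neither mentions a target lesion. Protocol 6.1 defines the measurement: "The Signs of AD score will be an examination of all lesions on the subject". SAP 6.9.1.1, the section that should analyse this endpoint, instead applies the ANCOVA to "The change from Baseline in the Signs of AD total score for the target lesion at Day 15, Day 29, and Day 57".

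**BSA, Days 15, 29 and 57.** SAP 5.1.3 gives these three days. SAP 6.9.1.2 repeats them and specifies an ANCOVA "with Baseline percent of total BSA affected by AD as covariate and treatment as factor". The shell, Table 14.2.3.3.1, is titled "Change from Baseline in Percent of Total BSA Affected by AD at Days 15, 29 and 85". Its rows are Day 29 and Day 57 on the first page and Day 57 again on the second. The footnote on both pages reads "Least squares mean, standard deviation, and p-value from an analysis of covariance with baseline Total Signs of AD and treatment as covariates". Tables 14.2.3.3.2 and 14.2.3.3.3 repeat this shell for the mITT and PP populations.

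**Target lesion, Days 29, 57 and 85.** This is a separate exploratory endpoint in SAP 5.1.3, with its own ANCOVA in 6.9.1.4. Table 14.2.3.7.1 is titled "Change from Baseline in Signs of AD Total Score at Target Lesions at Days 29, 57 and 85", but its second page shows Day 29 again and no row for Day 85.

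**The concern.** These are current method statements and programming shells, and for three exploratory endpoints they disagree with the endpoint list or with each other. Read literally, the method text never specifies an ANCOVA for the all-lesion Signs score at Days 15, 29 and 57. It gives that model to a different variable, measured in a subset of sites. The exploratory BSA shell would drop the Day 15 comparison, print Day 57 twice and adjust for a covariate that the method text does not name. The target-lesion shell would drop Day 85.

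At stake is whether the exploratory results reported are the ones that were planned. If the conflicts are found only after unblinding, someone must choose between competing instructions with the data in view.

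**Working it through.** The plan states no figure for this point, so the check sets endpoint, method text and shell side by side.

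| Item | Endpoint list | Method text | Shell | Where the error lies |
|---|---|---|---|---|
| Signs | SAP 5.1.3, Protocol 3.2: Signs score, Days 15, 29, 57 | 6.9.1.1: target lesion, Days 15, 29, 57 | 14.2.3.1.1: Signs total score, Days 15, 29, 57, no target-lesion limit | Text |
| BSA | SAP 5.1.3: Days 15, 29, 57 | 6.9.1.2: same days, baseline BSA | 14.2.3.3.1: title 15, 29, 85; rows 29, 57, 57; baseline Signs | Shell |
| Target lesion | SAP 5.1.3: Days 29, 57, 85 | 6.9.1.4: same days | 14.2.3.7.1: title 29, 57, 85; rows 29, 57, 29 | Shell |

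1. **BSA days.** Required {15, 29, 57}. The title {15, 29, 85} adds Day 85 and loses Day 57. The rows {29, 57, 57} lose Day 15. Title and rows disagree with the endpoint and with each other.

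2. **BSA covariate.** The Day 85 secondary BSA shell (14.2.2.3.1) names baseline BSA, so the exploratory footnote looks like a carry-over from a Signs table. SAP 6.1.4 does not settle the matter. It names baseline BSA for the secondary BSA endpoint only, baseline Signs for the Signs endpoints, and then rules out any other covariate. For exploratory BSA it therefore conflicts with 6.9.1.2 as well.

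3. **No single source is safe.** Working from the text alone gets Signs wrong. Working from the shells alone gets BSA and the target lesion wrong.

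4. **The Signs error would not announce itself.** Target lesions are also scored at Day 15 (Protocol 6.3.4 and Table 4), so the wrong model would run on real data at every listed visit.

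5. **Not a recorded decision.** SAP Section 8 lists the changes to the planned analyses. None of these differences is among them.

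6. **Scale, illustration only.** Let f be the share of subjects at photography sites (not given in the documents), the same in both arms, and assume equal residual SD for the two scores. With 100 per arm planned, n = 100f per arm. The standard error ratio is 1/√f. The difference detectable with 80% power at two-sided 0.05 (both assumed; the plan has no power calculation) is (1.960 + 0.842) × √(2/n), in SD units.

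| f | n per arm | 1/√f | Detectable difference (SD) |
|---|---|---|---|
| 1.00 | 100 | 1.00 | 0.40 |
| 0.75 | 75 | 1.15 | 0.46 |
| 0.50 | 50 | 1.41 | 0.56 |
| 0.25 | 25 | 2.00 | 0.79 |

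**The case against.** For each slip the right specification stands elsewhere in the same SAP. For Signs, the endpoint list, the heading of 6.9.1.1, the covariate section and the shell all point to the unrestricted score, and a programmer working from Table 14.2.3.1.1 would be correct. For BSA, the endpoint list and 6.9.1.2 are correct, and a shell whose title and rows disagree should be caught in routine review. For the target lesion, the shell's own title includes Day 85. This stands. A reader might infer that the programmed analyses are bound to miss their endpoints, but the documents support only that they could.

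Three other stronger readings also fail:

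- *All BSA shells are wrong.* Only 14.2.3.3.1 to 14.2.3.3.3 are. The Day 85 secondary shells have the right day and covariate, and the by-visit summaries (14.2.3.4.x) still report Day 15 BSA change descriptively.
- *Baseline Signs is a useless covariate for BSA.* No document gives its correlation with BSA change. It is a pre-treatment severity measure, and randomization still protects the comparison. The cost is departure from the stated model and perhaps some precision.
- *Intervals for Signs would be 1.4 to 2 times wider.* That needs 25 to 50% of subjects at photography sites and equal residual SD. Equal SD is doubtful: Protocol 4.1 requires a target lesion to score 6 to 12 at Baseline and sets no such limit on the all-lesion score. The figure also says nothing about the BSA errors.

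The objection does not remove the conflict. The errors lie in the text for one endpoint and in the shells for two, so no rule of precedence between them resolves everything, and the BSA footnote is not an obvious typing slip to someone working from the shell.

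**Conclusion.** The inconsistencies are real and can be checked within the documents. The text of 6.9.1.1 names the wrong variable. Shells 14.2.3.3.x have wrong days and the wrong covariate. Shells 14.2.3.7.x miss Day 85. A programmer who follows text or shells alone could run at least one exploratory analysis on the wrong variable, covariate or visit.

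The consequence is small. Only exploratory endpoints are involved, all testing is declared exploratory without Type I error adjustment, and these slips do not touch the primary or Day 85 secondary analyses. The conclusion rests on comparing passages and needs no numerical assumption. Any loss of precision from restricting Signs to the target lesion cannot be quantified from the documents. This is a drafting correction worth making, not a flaw in the design.

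**What to change.** Before the randomization schedule is released:

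- In SAP 6.9.1.1, delete the target-lesion qualifier so that the ANCOVA applies to the all-lesion Signs total score.
- In Tables 14.2.3.3.1 to 14.2.3.3.3 and their index entries, change the title to Days 15, 29 and 57, make the rows match, and name baseline total BSA as the covariate in the footnote.
- In Tables 14.2.3.7.1 to 14.2.3.7.3, replace the repeated Day 29 with Day 85.
- In SAP 6.1.4, extend the baseline BSA covariate to the exploratory BSA endpoint, so that it agrees with 6.9.1.2.

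The cost is text and shell edits. No new data, design change or additional analysis is needed.
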